Study Protocol and Statistical Analysis Plan

PDS (polydioxonene suture) versus prolene (polypropylene suture) as suture material for vaginal sacrospinous hysteropexy – a randomised controlled study

10.05.23

2079/2022

Medical University of Vienna

1. Introduction

Lifetime risk for pelvic organ prolapse (POP) is high and around 3-6% of symptomatic POP are associated with symptoms connected to a decisive lower quality of life, including bladder and bowel issues as well as sexual dysfunction [1,2]. Therefore, these women should be offered feasible, safe, and functional treatment options. Individual treatment plans based on patient's expectations wishes and necessities should be chosen. Treatment options can range from conservative pessary application to various surgical repair methods [3,4], with 11-19% in women reported to be undergoing surgery for prolapse or incontinence [5]. As women have expressed more and more the desire to keep their uterus, uterine-preserving procedures such as vaginal sacrospinous hysteropexy (SSH) have become an increasingly utilized surgical option for the primary treatment of POP [3]. Sacrospinous hysteropexy is an uterine-preserving, well established surgical procedure that gained popularity after the publication of the SAFE U trail conducted by the Dutch research group of Detollenaere and Schulten et al. about its successful use [6,7]. Furthermore, several studies investigated the surgical outcomes after the different types of surgery and concluded that compared with vaginal hysterectomy with apical fixation, SSH has similar or possibly even better outcomes [8–10]. As such it has also become the most commonly performed uterine-preserving surgical technique at our institution.

However, it is crucial also to identify surgical variables that may have an impact on the outcomes of prolapse surgery: especially as the scientific evidence guiding the choice of suture material in sacrospinous hysteropexy is scant. In their SAFE U trail Detollenaere et al. used prolene as suture material, however patients reported buttock pain for some time after the intervention [6]. At our institution we mainly use

PDS sutures as a late resorbable suture material and noticed no such claims from patients.

The aim of this RCT is to investigate the effects of resorbable (PDS) versus non-resorbable (prolene) suture material in patients with symptomatic POP undergoing vaginal sacrospinous hysteropexy.

2. Experimental Plan

2.1 Study hypothesis

Primary study hypothesis is that patients receiving a sacrospinous hysteropexy with non-resorbable Prolene sutures (study group) experience a better subjective symptom improvement (evaluated by the prolapse domain score of the Deutscher Beckenboden Fragebogen [11]) assessed at 12 months after surgery, than patients with resorbable PDS sutures (control group).

The secondary hypotheses are, that the study group will have:

- better anatomical outcomes (better rate anatomical outcome in each compartment (change in POP-Q values from baseline) [12]),
- better condition-specific quality of life scores (changes in questionnaire from baseline),
- less postoperative complications (haematoma, vesico-vaginal fistula, ureteral obstruction, urinary tract infection, incomplete bladder emptying, overactive

bladder or stress incontinence symptoms, suture erosion, vaginal wound dehiscence, infection or granulation tissue, etc),

- lower use of pain killers for buttock pain during the hospital stay and in the 12 months postoperative period
- lower pain levels (assessed through the standardised Visual Analog Scale (VAS) and Numeric Rating Scale (NRS) [13]) at postoperative day 1, at discharge, at 4 to 6 weeks, 6 and 12 months.

2.2 Study design

This trial is a single-centre, prospective, randomized trial conducted with the aim of determining the superiority of non-absorbable prolene over absorbable PDS suture material with regard to the primary outcome in POP patients undergoing sacrospinous hysteropexy. The study will be a single-blind study, as it is impossible to blind the study surgeon for the surgical procedure to which the subject is assigned. However, all outcome assessors and the subjects will be blinded to the assigned treatment. Postoperative follow-up will take place after 4-6 weeks, 6 months and 12 months. Patients will undergo a standardized urogynaecologic examination that includes assessment of prolapse with POP-Q measurement [12]. Furthermore subjective outcome will be assessed with standardized questionnaires – our study participants will receive the German version of the pelvic floor questionnaire [11].

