2.5 Randomization

Randomization will be performed by the randomizer of the Medical University of Vienna; subjects will be stratified by parity (Primipara / Multipara) and randomized in blocks of four. All subjects will receive a unique study number.

To prevent unmasking the actual procedures, the medical records will indicate the actual surgical procedure without stating the suture material used for anterior colporrhaphy. Intraoperative data collection will be conducted by the study surgeon rather than by other research staff.

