2.6 Intervention

Sacrospinous hysteropexy will be performed in a traditional and standardized manner in accordance with our surgical policy. Any other concomitant procedures (e.g.,

anterior and/or posterior colporrhaphy, cystoscopy, etc.) will be performed in accordance with each surgeon's preferred technique.

Operative management: All patients will be operated by the vaginal route. They are prepared under strict aseptic conditions in the dorsal lithotomy position. The bladder is emptied preoperatively with a thin disposable catheter and antibiotic prophylaxis (cefazolin) is administered before incision. A vasoconstricting solution (combination of vasopression and NaCl) is administered and a high posterior colpotomy is made towards the posterior cervix. Blunt preparation towards the right Spina ischiadica to visualize the right sacrospinous ligament. Once 4 cm of ligamentum sacrospinale are visualised, two sutures will be placed through the ligament approximately 2 cm medial of the spina ischiadica. Depending on preoperative randomization, patients will receive either PDS sutures (PDS 0) or prolene (2-0) sutures. This suture will then be placed through the posterior cervical wall, but not yet knotted. First, the colpotomy will be closed via absorbable sutures (2/0 vicryl). Should additional procedures such as anterior and/or posterior colporrhaphy be indicated, they will be performed at this stage. Only after, the pre-laid fixation sutures will be tied, whereby the portio will come to lie about 4-6 cm cranial of the level off the vulva towards the sacrospinous ligament. Participating surgeons will be defined as high volume surgeons in prolapse surgery and will also be part of the urogynaecologic core team.

Perioperative management: is also standardized and includes preoperative single-shot antibiotics as well as vaginal pack and an indwelling urinary catheter for 24 hours after the surgical procedure. Patients will have postvoid residual volume measurement at the first postoperative day (when urinary catheter is removed). A postvoid residual volume of $2 \times < 150$ ml is defined as normal and no further follow-ups are necessary. Postvoid residual volumes of > 150 mL or greater will be

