Furthermore, patients will answer the "Patient Global Impression of Improvement (PGI-I)" as it takes little effort for the patient and allows a precise result in terms of the rate of improvement after the operation [15]. One of the following answers can be given by each patient:

1. A lot better.
2. Much better.
3. A little better.
4. no change.
5. A little worse.
6. Much worse.
7. A lot worse.

Scheduled in-person follow-ups will occur at 4 to 6 weeks, 6 and 12 months after the operation. Each check-up will include a full urogynaecologic clinical examination including POP-Q, ultrasound and bloodwork as well as a written questionnaire identical to the one at baseline. In addition, an update of current medications, an assessment of new or continuing pelvic floor disorders and adverse events that occurred since the previous evaluation will be obtained by the study coordinator at each visit. All data will be anonymized and collected using case report forms by examiners or trained research coordinators who are blinded to the treatment assignment.

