2.8 Primary and secondary outcome measures

The primary outcome is subjective symptom improvement (evaluated by the prolapse domain score of the Deutsche Beckenboden Fragebogen) assessed at 12 months after surgery.

The secondary outcomes are the anatomical outcomes (the rate of suboptimal anatomical outcome in each compartment (POP-Q point, change in POP-Q values from baseline), condition-specific quality of life (any changes in questionnaire Deutscher Beckenboden Fragebogen from baseline), postoperative complications (haematoma, vesico-vaginal fistula, ureteral obstruction, urinary tract infection, incomplete bladder emptying, overactive bladder or stress incontinence symptoms, suture erosion, vaginal wound dehiscence, infection or granulation tissue, etc), and use of pain killers during the hospital stay. In addition, patients' pain level will be assessed through the standardised Visual Analog Scale (VAS), Numeric Rating Scale (NRS) [13] and the earlier specified questions, patients' improvement rate will be assessed through the "Patient Global Impression of Improvement (PGI-I).

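### The plan states that assessors and patients are blinded, but nothing protects this at the follow-up pelvic examination, where the suture could plausibly be recognised

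*Combined protocol and SAP*

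**What the plan says.** Section 2.2 calls the trial single-blind because the surgeon cannot be masked, and continues: "However, all outcome assessors and the subjects will be blinded to the assigned treatment". Section 2.8 (Data collection) repeats the claim for follow-up, with data "collected using case report forms by examiners or trained research coordinators who are blinded to the treatment assignment". Neither place says how the masking is kept up.

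The one procedure described is in 2.5: the medical record gives the operation "without stating the suture material used for anterior colporrhaphy".

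Section 2.6 gives the surgical sequence. After passing through the sacrospinous ligament: "This suture will then be placed through the posterior cervical wall, but not yet knotted". Then: "First, the colpotomy will be closed via absorbable sutures (2/0 vicryl". Any additional repair follows, and "Only after, the pre-laid fixation sutures will be tied". The materials are PDS 0 and prolene 2-0. Section 1 calls PDS late resorbable and prolene non-resorbable.

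On the visits at 4 to 6 weeks, 6 months and 12 months, 2.8 (Data collection) says: "Each check-up will include a full urogynaecologic clinical examination including POP-Q, ultrasound and bloodwork as well as a written questionnaire". The listed complications in 2.8 (Primary and secondary outcome measures) include "suture erosion, vaginal wound dehiscence, infection or granulation tissue". The primary outcome is the patient-reported prolapse domain score at 12 months.

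**The concern.** A masking statement is only as good as the procedure behind it. Here the person said to be masked examines the area where the trial suture was placed and must look for suture-related findings. Leaving the material out of the record does not help if it can be seen or felt.

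Two groups of outcomes are at stake. POP-Q measurements and complication recording rest on the examiner's judgement and are exposed directly. The prolapse domain score, the follow-up VAS/NRS and pain questions, and the PGI-I are answered by the woman. They are exposed only if she learns or infers something from the examiner before she answers.

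Expectations are also not neutral. Section 2.1 hypothesises that prolene is better, while section 1 links prolene to buttock pain reported in a cited trial and says that no such complaints were noticed with PDS at this institution. Someone who recognises the material may hold different expectations for different outcomes.

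**Working it through.** No figure in the plan bears on this point and the sample size is unaffected, so the check sets the passages side by side.

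1. **Is a method of masking at the examination given?** No. Sections 2.2 and 2.8 state that assessors are masked. Section 2.5 deals with the record alone, and with the suture of a different procedure. Read literally, it would let the record name the hysteropexy suture.

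2. **Could the material be recognised?** By 2.6, the suture goes through the posterior cervical wall, the colpotomy is closed, and only then are the fixation sutures tied. Tying after closure makes a knot on the vaginal side a natural reading, and no burying step is described. Equally, no passage says that the knots are exposed or palpable.

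3. **Would recognition separate the arms?** One material resorbs and the other does not, so a suture that persists late would suggest prolene. The plan gives no resorption time for PDS. At 4 to 6 weeks, and possibly at 6 months, suture may be present in both arms, although the different calibres could be a cue even then. The contrast should be greatest at 12 months, when the primary outcome is taken.

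4. **Must the examiner look?** Yes. Each follow-up visit includes a full pelvic examination, and suture erosion and granulation tissue are recorded.

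5. **Is the questionnaire shielded from the examination?** No. Both belong to the same visit and no order is given. Nothing restrains remarks about the suture, and no check of masking is planned.

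6. **Which outcomes are reached, and how?** POP-Q and complications: one step, recognition. Patient-reported scores at follow-up: recognition, then a remark before completion, then a changed answer. Pain on postoperative day 1 and at discharge precedes every follow-up visit and is not reached by this route.

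**The case against.** The strongest objection is that the premise is not in the documents. They do not say where the knots lie, whether they are covered, or when PDS is gone, and the plan twice says that the staff are masked. The primary outcome is a written questionnaire that the examiner does not score, so bias in it needs several undocumented steps in a row. This stands, and it limits the point to a gap in protection.

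Stronger readings are tempting, but the documents do not support them:

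- **That blinding fails, or that the primary result will be biased.** Recognition is plausible, not shown, and disclosure to the patient is neither described nor forbidden.
- **That the examination comes before the questionnaire.** The sentence in 2.8 lists what a visit contains and does not set a sequence.
- **That only the prolene arm would be affected.** If a persisting knot suggests prolene, its absence suggests PDS, so expectations could act in both arms.
- **That the bias can be sized.** Any recognition rate or score shift would be invented.

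It might also seem sensible to have POP-Q recorded before the cervix is inspected. That is not workable, because POP-Q includes the apical point C, which 2.7 uses for eligibility.

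What the objection does not answer is that the masking is asserted without a procedure at the one place where it is most open to challenge, and that the only written step names the wrong suture.

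**Conclusion.** The point holds as a gap in the plan. Masking of assessors and patients is stated but not protected at the follow-up examination, and the record-masking sentence in 2.5 does not cover the suture under comparison.

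The direct risk is to POP-Q and complication recording. The risk to the primary, follow-up pain and PGI-I scores is indirect. Direction and size are unknown, and the documents give no basis for estimating either. The wording error in 2.5 can be read off the page. The recognition route rests on the assumption that some suture can be seen or felt at the cervix, and for late visits that PDS has largely gone by then.

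This is worth acting on because the remedy is nearly free and does not depend on proving that assumption. It is not a reason to doubt the design as a whole.

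**What to change.** - **2.8 (Data collection).** At every follow-up visit, the woman completes and hands in the pelvic floor questionnaire, VAS/NRS, pain questions and PGI-I before any examination or discussion. Examiners do not mention the suture material except where her care requires it.
- **2.5.** Reword the masking sentence so that the record omits the hysteropexy suture material.
- **2.2.** Describe examiner masking as intended rather than assured.
- **Optional.** Record the examiner's and the woman's guess of the allocation at 12 months and report them by arm. The woman's guess will partly reflect how well she feels, so it is weak evidence of unmasking.

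The order of visits protects the patient-reported outcomes. It cannot mask an examiner who recognises the suture, which is why the wording in 2.2 should change as well. The cost is a visit-order instruction, two wording changes and a few minutes per visit. No extra staff are needed and no treatment changes.

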2.3 Study setting

This study will be conducted at the urogynaecologic outpatient clinic (Division of General Gynaecology and Gynaecologic Oncology, Department of Obstetrics and

Gynaecology, Medical University of Vienna). Enrolment, treatment, and data collection will be standardized by all sites according to the approved study protocol.

2.4 Participants and recruitment

The study population will consist of women aged 18 years or older who are referred to our urogynaecologic outpatient clinic due to symptomatic POP. Women with anterior vaginal wall prolapse and an indication for reconstructive pelvic floor surgery – including sacrospinous hysteropexy – can be included in this trial.

2.5 Randomization

Randomization will be performed by the randomizer of the Medical University of Vienna; subjects will be stratified by parity (Primipara / Multipara) and randomized in blocks of four. All subjects will receive a unique study number.

To prevent unmasking the actual procedures, the medical records will indicate the actual surgical procedure without stating the suture material used for anterior colporrhaphy. Intraoperative data collection will be conducted by the study surgeon rather than by other research staff.

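### A printed, fixed block length of four in one centre with unblinded surgeons lets anyone who knows all earlier allocations in a stratum foresee up to one third of them on average; use varying, undisclosed blocks

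*Combined protocol and SAP*

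**What the plan says.** Section 2.5 assigns the task to a university service ("Randomization will be performed by the randomizer of the Medical University of Vienna") and specifies one block length: "subjects will be stratified by parity (Primipara / Multipara) and randomized in blocks of four". No other length is mentioned.

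Section 2.2 describes the setting: "This trial is a single-centre, prospective, randomized trial". On blinding it says that "it is impossible to blind the study surgeon for the surgical procedure to which the subject is assigned", whereas "all outcome assessors and the subjects will be blinded to the assigned treatment". Section 2.6 adds: "Participating surgeons will be defined as high volume surgeons in prolapse surgery and will also be part of the urogynaecologic core team". It also places randomization before the operation ("Depending on preoperative randomization, patients will receive either PDS sutures (PDS 0) or prolene (2-0) sutures") but gives no interval between consent, allocation and surgery.

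Section 2.5 contains one measure to mask the records: "the medical records will indicate the actual surgical procedure without stating the suture material used for anterior colporrhaphy". As worded, this covers the colporrhaphy suture. The randomised suture is the one used for the hysteropexy.

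The documents do not state who enrols patients, whether that person can see earlier allocations, or whether eligibility and baseline data are fixed before an allocation is released.

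**The concern.** With a known, constant block length, a person who has followed the allocations in a stratum can count to the end of each block. A central randomizer hides the list, but it does not prevent this counting. Several conditions that make counting possible are present: one centre, two strata, a published block length, and operators from one team who know which suture they used.

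Entry under section 2.7 depends partly on a clinical decision, namely that sacrospinous hysteropexy is planned, and the timing of such a decision can be moved. If someone foresaw the next allocation, women with better or worse prospects could be brought forward or deferred, knowingly or not. The arms would then differ at baseline in expected improvement. Blinding of patients and assessors protects the measurement of the outcome, not the composition of the arms. The planned t-test or Mann-Whitney test of the primary outcome (section 2.10) adjusts for nothing and could not repair such a difference.

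**Working it through.** **Inputs.** Block length 4 and two parity strata (section 2.5). From section 2.9: 26 women per group, 21 per group after 20% dropout, SD of change 2.2, target difference 2. Significance level 0.05 (section 2.10), taken as two-sided because the side is not stated. The 1:1 ratio is implied by the equal groups.

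**The plan's own figures.** SD of change = √(2 × 2.2² × (1 − 0.5)) = 2.2. A two-sided t-test with 21 per group and a difference of 2 has power 0.82, consistent with the stated 80%. With 26 enrolled, 26 × 0.8 = 20.8, or about 21 analysed. The present point does not affect the sample size. The plan gives no figure for predictability.

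**Certain allocations, all earlier ones known.** A balanced block of four has 6 sequences. AABB and BBAA fix positions 3 and 4; the other four fix position 4 only.
- Expected number certain = (2 × 2 + 4 × 1)/6 = 1.33 of 4, or 33.3%.
- For 52 women in 13 complete blocks: 13 × 1.33 = 17.3.
- With two strata of 26 (assumed), each has 6 complete blocks and 2 women over: 2 × 6 × 1.33 = 16, and 16/52 = 31%.

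**Best guess.** Guessing the arm with more places left is right with probability 1/2, 2/3, 2/3 and 1 at positions 1 to 4. The mean is 2.83/4 = 70.8%.

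**Less than full knowledge (block position still known).**
- Latest allocation unknown: only position 4 can be certain, and only if positions 1 and 2 match (2 of 6 sequences). (1/3)/4 = 8.3%.
- Latest two unknown: 0%.
- Each earlier allocation known with probability 75%, 50% or 25% (assumed): about 19%, 8% and 2% by simulation.

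**Effect of steering (assumed behaviour).** Suppose there is no true effect, steering happens only on certain allocations, and it always favours the same arm. Let c be the contrast in expected change between women steered to one arm and women steered to the other, that is ±c/2. One third of each arm is steered, so bias = (1/3)(c/2) + (1/3)(c/2) = c/3. The standard error is 2.2 × √(2/26) = 0.61 with 26 per arm and 2.2 × √(2/21) = 0.68 with 21.

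| Contrast c | Bias c/3 | Type I error, 26 per arm (simulated) |
|---|---|---|
| 0.5 (±0.25) | 0.17 | about 6% |
| 1 (±0.5) | 0.33 | about 8% |
| 2 (±1) | 0.67 | about 18% |

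With 21 analysed per arm, the 2-point contrast gives about 15–16%.

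**Varying blocks.** With lengths 4, 6 and 8 mixed at random and unknown to the recruiter, simulation of two strata of 26 leaves about 2% of allocations certain. Best guesses are still right 67–68% of the time.

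**The case against.** A reader might infer that the design by itself makes one third of allocations certain in advance, and that the trial is therefore biased. The documents do not support that. One third is an upper-end average. It requires knowledge of every earlier allocation in the stratum and of the position in the block. Section 2.2 says only that the study surgeon cannot be blinded. No section says that surgeons enrol patients, how many there are, or that they see one another's allocations. Membership of one core team does not establish this. Section 2.8 also has data collected by blinded staff, so not everyone in the clinic knows the arms. If women are randomised some time before surgery and the suture becomes known only in theatre, recent allocations stay hidden and the share drops to 8% or to zero.

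The larger type I errors also call for care. The 18% figure needs a contrast of 2 points between women steered to the two arms, which equals the whole difference the trial is designed to detect, and steering that always runs in one direction. Nothing in the documents suggests such conduct.

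These objections limit the size of the concern and make it conditional. They do not remove it. The fixed length is printed, no described safeguard restricts knowledge of past allocations for whoever enrols, and the record-masking sentence as written does not reach the randomised suture.

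**Conclusion.** The point holds in a conditional form. The design permits foresight of up to one third of allocations on average (about 31% with incomplete blocks in two strata) for someone with full knowledge of the stratum, and much less with partial knowledge. The arithmetic is firm. The exposure is unknown, because the documents do not describe who enrols or what they see, and steering is purely an assumption. Under modest assumed steering the type I error would move from 5% to about 6–8%. Figures in the upper teens need an extreme contrast. This is a cheap preventive improvement to a design choice, not evidence of bias and not an error in the analysis.

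**What to change.** In section 2.5, replace the fixed blocks of four with randomly varying block lengths (for example 4, 6 and 8) set in the university randomizer. Keep the lengths out of the protocol and away from recruiting and operating staff. Release each allocation only after consent, eligibility and the baseline questionnaire are locked, as close to surgery as possible. State who enrols, and that this person has no access to earlier allocations.

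The second half matters at least as much as the first. Varying blocks nearly remove certain knowledge, but the best-guess rate falls only from about 71% to 67–68%.

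The cost is a randomizer setting and a few sentences, with no effect on the sample size. The downside is a possible imbalance of up to 4 rather than 2 women per stratum if recruitment stops inside a block.

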2.9 Sample size and power considerations

Alteration of the prolapse domain score obtained from the pelvic floor questionnaire before and after intervention (between baseline and 12 months follow-up) will be compared between patients receiving continuous stitches versus simple interrupted stitches for anterior colporrhaphy. Schoenfeld et al. observed a mean prolapse domain score of 3.33 with a standard deviation of 2.2; we assume that the standard deviation of the pre- and post-interventional treatment will be equal, and that the correlation between the two values is 0.5, resulting in a standard deviation of the change between pre- and post-interventional value will be 2.2.; then, with 21 patients per group a difference of 2 between the changes in the two groups can be identified

with 80% power. Taking into account an expected dropout rate of 20%, 26 patients will be included per group.

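### The masking rule in section 2.5 withholds the anterior colporrhaphy suture, not the randomised hysteropexy suture, so followed literally it lets the medical record show the allocation

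*Combined protocol and SAP*

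**What the plan says.** Section 2.6 (Intervention) defines what is randomised: "Depending on preoperative randomization, patients will receive either PDS sutures (PDS 0) or prolene (2-0) sutures". These sutures pass through the sacrospinous ligament and then the posterior cervical wall. Anterior colporrhaphy appears in the same section as a possible additional operation: "Should additional procedures such as anterior and/or posterior colporrhaphy be indicated, they will be performed at this stage". Its technique is left to the individual surgeon.

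Section 2.2 (Study design) commits to masking: "all outcome assessors and the subjects will be blinded to the assigned treatment". Section 2.8 (Data collection) adds that case report forms are completed by "examiners or trained research coordinators who are blinded to the treatment assignment".

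Section 2.5 (Randomization) gives the practical measures, introduced as a means of preventing unmasking. The first concerns the record: "the medical records will indicate the actual surgical procedure without stating the suture material used for anterior colporrhaphy". The second concerns who records data in theatre: "Intraoperative data collection will be conducted by the study surgeon rather than by other research staff".

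Section 2.9 (Sample size and power considerations) says that changes in the prolapse domain score "will be compared between patients receiving continuous stitches versus simple interrupted stitches for anterior colporrhaphy".

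**The concern.** A masking rule has to cover the piece of information that identifies the arm. Here that is the material of the fixation suture. The rule in 2.5 names the suture of a different, non-randomised procedure and is silent on the one that defines the groups.

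The outcomes are not equally exposed. POP-Q measurements and complications such as suture erosion or granulation tissue rely on examiner judgement, so they are most at risk if an assessor reads the operative report. The primary outcome, the prolapse domain score at 12 months, and the pain scores come from the patient. They are at risk only if she learns which suture she received, for example from a discharge letter.

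Expectations about the two materials already exist. The Introduction links prolene to reported buttock pain and says the institution has noticed no such complaints with PDS, while section 2.1 hypothesises less pain with prolene. Follow-up takes place in the outpatient clinic of the single centre, and the surgeons belong to its urogynaecologic core team. Blinding that has been lost cannot be restored at analysis.

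**Working it through.** The main point is textual, so the relevant provisions are set side by side.

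| Question | Section | Answer in the protocol |
|---|---|---|
| What is randomised? | 2.6 | Material of the hysteropexy fixation suture |
| Who must not know it? | 2.2; 2.8 Data collection | Patients, outcome assessors, data collectors |
| What is kept out of the medical record? | 2.5 | Suture material of anterior colporrhaphy |
| Is anterior colporrhaphy randomised, or done in everyone? | 2.6 | Neither: done if indicated, by the surgeon's own technique |
| Is the hysteropexy suture kept out of the record by any other rule? | None found | No |

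1. The colporrhaphy suture carries no information on allocation, so withholding it protects nothing.
2. For a woman who has no anterior colporrhaphy, the rule withholds nothing at all.
3. The fixation suture is placed in every participant. The planned number is 2 × 26 = 52 ("26 patients will be included per group"). The rule as worded covers the randomised suture in 0 of these 52.
4. Leaving theatre data to the surgeon protects the route by which study data are captured. It does not govern what an operative report or discharge letter says.
5. The blinding statements in 2.2 and 2.8 set the goal. They give no rule on the content of the record.

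**Does the wrong arm label in 2.9 affect the sample size?** Inputs from 2.9: SD 2.2 before and after surgery, correlation 0.5, difference 2, power 80%, 21 per group, dropout 20%. The significance level of 0.05 is from 2.10. A two-sided test is assumed, because the plan does not state sidedness.

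- SD of change = √(2.2² + 2.2² − 2 × 0.5 × 2.2 × 2.2) = √4.84 = 2.2, as the plan states.
- Standardised difference = 2 / 2.2 = 0.909.
- Two-sample t-test with 21 per group: noncentrality = 0.909 × √(21/2) = 2.95 on 40 degrees of freedom, giving power 82.0%.
- The n that gives 80% power is 20.002 per group, which rounds up to the plan's 21.
- Dropout: 26 × 0.8 = 20.8, just under 21. Dividing instead, 21 / 0.8 = 26.25, which strictly rounds up to 27. Power at 20 per group is 79.997%, so the shortfall is trivial and does not bear on this point.

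No input depends on what the arms are called. The label in 2.9 is wrong but has no numerical effect.

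**The case against.** The best defence is that the intention is plain. The rule is introduced as protection against unmasking, and the item it withholds is suture material, which is exactly this trial's randomised factor. Only the name of the procedure is wrong. Section 2.2 requires blinding of patients and assessors without exception, and silence about the hysteropexy suture is not permission to disclose it. A sensible surgeon would probably read the sentence as meant. No unmasking has been shown, the primary outcome is patient-reported, and the outcomes most exposed are secondary.

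Much of this stands. The protocol taken as a whole clearly intends the allocation to be hidden, and nothing in it says the record will be disclosed to assessors or patients. The claim is therefore limited to what the rule does if followed as written.

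The defence does not remove the error. The blinding statements are aims, and 2.5 is the only place that tells those writing the record what to leave out. It is also not the only place where the text describes a different comparison, since 2.9 does so too, so a reader cannot simply assume that the procedure names are reliable. It is likewise fair to say that a restricted record goes further than replacing the procedure name. The minimum correction is that replacement. The restricted record answers the practical question of where the information is then kept.

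**Conclusion.** The concern holds. The only rule on the content of the medical record names the wrong suture, so as written it does not protect the allocation of any of the 52 planned women. This is an operative instruction that is wrong, in a trial that commits to blinded patients and assessors, and it should be corrected.

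The conclusion rests on a literal reading of 2.5 and on the absence of any other rule on record content. The record can unmask, but it need not. The documents do not say whether assessors or patients see the operative report, and they give no basis for estimating a bias, so none is claimed. The mislabelled groups in 2.9 are a clerical matter: the stated 21 per group still gives 82.0% power under the plan's own assumptions.

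**What to change.** In section 2.5, replace the sentence on medical records with wording such as:

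> Medical records that assessors or patients can see, including the operative report and discharge letter, will not name the suture material used for the sacrospinous hysteropexy. The surgeon will enter it in a restricted file, which can be opened when safety requires it.

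In section 2.9, describe the groups as patients receiving PDS or prolene sutures for sacrospinous hysteropexy. The sample size calculation is not altered by this change.

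The cost is a short amendment to two sections, plus one restricted record to maintain with a defined access route. No extra patients or visits are needed.
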